Janssen Research & Development

Statistical Analysis Plan

**A Randomized, Double-blind, Placebo-controlled Phase 1/2a Study to Evaluate the Safety,
Reactogenicity, and Immunogenicity of Ad26COVS1 in Adults Aged 18 to 55 Years
Inclusive and Adults Aged 65 Years and Older**

Protocol VAC31518COV1001; Phase [1/2a]

VAC31518 (JNJ-78436735)

Status: Approved
Date: 8 September 2022
Prepared by: Janssen Vaccines & Prevention B.V.
Document No.: EDMS RIM-102684

Compliance: The study described in this report was performed according to the principles of Good Clinical Practice (GCP).
Confidentiality Statement

The information provided herein contains Company trade secrets, commercial or financial information that the Company customarily holds close and treats as confidential. The information is being provided under the assurance that the recipient will maintain the confidentiality of the information under applicable statutes, regulations, rules, protective orders or otherwise.

CHANGES TO PREVIOUS VERSIONS

Amendment 2 (8 September 2022)

This Statistical Analysis Plan (SAP) amendment relates to amendment 16 of the VAC31518COV1001 clinical trial protocol. In this amendment, the booster vaccination at 24 months after completion of the primary regimen is removed in Cohorts 2a (Target Visit Day 731) and 2b (Target Visit Day 787). This is reflected in section 7.1.2. “Phase Definitions”, and other sections where reference was made to that booster vaccination.

Amendment 1 (16 December 2021)

This Statistical Analysis Plan (SAP) amendment relates to amendment 15 of the VAC31518COV1001 clinical trial protocol, in which a single ad hoc booster vaccination with Ad26.COV2.S at the 5×10^{10} vp dose level is offered to all eligible study participants (as defined in the clinical trial protocol).

The SAP amendment describes the planned safety and immunogenicity analyses that will be conducted on study participants who elect to receive the ad hoc booster dose.

The following changes have also been applied during this SAP update:

- Throughout the SAP: references to “final analysis” have been removed since this analysis was removed from the protocol.
- Section **7.7.3**:
 - o The confidence interval method was changed from Clopper Pearson to Wald, because the Clopper Pearson confidence interval cannot be calculated for a relative risk.

TABLE OF CONTENTS

CHANGES TO PREVIOUS VERSIONS.....	2
TABLE OF CONTENTS	3
LIST OF TABLES	4
VERSION HISTORY.....	5
1. INTRODUCTION.....	6

Table 1: Phase Definitions for Cohorts 1a, 1b, and 3	8
Table 2: Phase Definitions for Cohort 2a.....	9
Table 3: Phase Definitions for Cohort 2b	10
Table 4: Demographic Variables.....	13
Table 5: Summary of Humoral Immunogenicity Assays	22
Table 6. Summary of Cellular Immunogenicity Assays	23

VERSION HISTORY**SAP Version History Summary**

SAP Version	Approval Date	Change	Rationale
1	20-Aug-2020	Not Applicable	Initial release
2	16-Dec-2021	Cf. Section “Changes to Previous Versions”	Amendment to clinical trial protocol; addition of exploratory immunogenicity analyses, including non-inferiority analyses and alternative responder definitions; other minor updates
3	7 September 2022	Cf. Section “Changes to Previous Versions”	Amendment to clinical trial protocol

1. INTRODUCTION

This Statistical Analysis Plan (SAP) describes the pre-planned analyses for the Data Review Committee (DRC), Interim Analyses, Primary Analyses, and End of Study Analysis, for all cohorts in the study. One or several Data Presentation Specification Documents (DPS) will be available to further detail the statistical outputs that will be generated.

For some analyses (e.g. RNA sequencing data, passive transfer study), a separate SAP may be written.

2. OBJECTIVES AND ENDPOINTS

Refer to Clinical Trial Protocol (CTP) Section 3.

3. TRIAL DESIGN

Refer to CTP Section 4.

4. STATISTICAL HYPOTHESES

Refer to CTP Section 9.1.

5. SAMPLE SIZE DETERMINATION

Refer to CTP Section 9.2.

6. POPULATIONS FOR ANALYSIS

For vaccine studies, study intervention assignment will follow the as treated principle: all analyses (including safety, immunogenicity and efficacy analyses) will be analyzed by the actually received vaccine.

Population	Description
All screened participants (ALL)	The “all screened participants” set includes all participants that were screened, regardless of whether they were enrolled and/or randomized.
All randomized participants (ALL RANDOMIZED)	The “all randomized participants” set includes all participants that were randomized to one of the treatment groups.
Full Analyses Set (FAS)	The full analysis set will include all participants with at least one vaccine administration documented.
Per Protocol Immunogenicity Set (PPI)	The per protocol immunogenicity population will include all randomized and vaccinated participants for whom immunogenicity data are available excluding participants with major protocol deviations expecting to impact the immunogenicity outcomes. In addition, samples obtained after missed vaccinations or participants with natural infection occurring after screening (if applicable) will be excluded from the analysis set.
Per Protocol Efficacy Set (PPE)	The per protocol efficacy population will include all randomized participants having received at least 1 vaccination for whom efficacy data concerning endpoint measures are available. All efficacy analyses will be done according to the as treated principle (ie, actually received vaccinations).

7. STATISTICAL ANALYSES

7.1. General Considerations

7.1.1. Study Phases

A baseline (or reference) value will be defined as the value of the last available assessment prior to the first vaccination on Day 1.

The safety analysis will present all results by phase (cf. section 7.1.2 for phase definitions). Immunogenicity results will be presented per scheduled time point as appropriate. Efficacy analyses will present results by phase or pooled for the entire study, as appropriate. Listings will be shown per phase and time point.

Study day or relative day is defined as follows:

Study Day = visit date - date of Day 1 + 1; if visit date \geq date of Day 1 (date of first vaccination).

Study Day = visit date - date of Day 1; if visit date $<$ date of Day 1 (date of first vaccination).

7.1.2. Phase Definitions

The phase definitions are different by cohort. For cohorts in which two vaccinations are administered in the primary regimen and having no booster doses (cohorts 1a, 1b and 3), the phases in the study will be constructed as detailed in [Table 1](#).

Table 1: Phase Definitions for Cohorts 1a, 1b, and 3

Phase	Phase #	Period	Period #	Interval	
				From	To
Screening	1			Date and time of signing the informed consent form	One minute prior to start of post dose 1 period
Regimen	2	Post-dose 1	1	Date and time of first vaccination	
Minimum of:
 
 a) 23:59 at the date of last contact (for early discontinuation) b) 23:59 at the date of database cut-off in case of interim analysis c) 23:59 on 28 days after the first vaccination (23:59 of day of vaccination + 28 days) d) One minute prior to post-dose 2
Follow-up 1	3			One minute after Post dose 1 period end	
Minimum of:
 
 a) 23:59 at the date of last contact (for early discontinuation) b) 23:59 at the date of database cut-off in case of interim analysis c) One minute prior to post dose 2
Regimen	2	Post-dose 2	2	Date and time of second vaccination	
Minimum of:
 
 a) 23:59 at the date of last contact (for early discontinuation) b) 23:59 at the date of database cut-off in case of interim analysis c) 23:59 on Day 28 after the second vaccination (23:59 of day of vaccination + 28 days)
Follow-up 2	4			One minute after Post-dose 2 period end	
Minimum of:
 
 a) 23:59 at the date of last contact (for early discontinuation) b) 23:59 at the date of database cut-off in case of interim analysis c) 23:59 at the date of last visit

Note: the end date of the regimen phase should be the end date of the last post dose period.

For cohort 2a, the phases will be defined as detailed in [Table 2](#).

Table 2: Phase Definitions for Cohort 2a

Phase	Phase #	Period	Period #	Interval	
				From	To
Screening	1			Date and time of signing the informed consent form	
Regimen	2	Post-dose 1	1	Date and time of first vaccination	Minimum of: a) 23:59 at the date of last contact (for early discontinuation) b) 23:59 at the date of database cut-off in case of interim analysis c) 23:59 on 28 days after the first vaccination (23:59 of day of vaccination + 28 days) d) One minute prior to post-dose 2
Follow-up 1	3			One minute after Post dose 1 period end	Minimum of: a) 23:59 at the date of last contact (for early discontinuation) b) 23:59 at the date of database cut-off in case of interim analysis c) One minute prior to post booster 1
Regimen	2	Post-booster 1	2	Date and time of first booster vaccination	Minimum of: a) 23:59 at the date of last contact (for early discontinuation) b) 23:59 at the date of database cut-off in case of interim analysis c) 23:59 on Day 28 after the first booster vaccination (23:59 of day of vaccination + 28 days)
Follow-up 2	4			One minute after Post-booster 1 period end	Minimum of: a) 23:59 at the date of last contact (for early discontinuation) b) 23:59 at the date of database cut-off in case of interim analysis c) One minute prior to post booster 2
Regimen	2	Post-booster 2	3	Date and time of second booster vaccination	Minimum of: a) 23:59 at the date of last contact (for early discontinuation) b) 23:59 at the date of database cut-off in case of interim analysis c) 23:59 on Day 28 after the second booster vaccination (23:59 of day of vaccination + 28 days)
Follow-up 3	5			One minute after Post-booster 2 period end	Minimum of: a) 23:59 at the date of last contact (for early discontinuation) b) 23:59 at the date of database cut-off date in case of interim analysis c) 23:59 at the date of last visit

Note: the end date of the regimen phase should be the end date of the last post dose period.

For cohort 2b, the phases will be defined as detailed in [Table 3](#).

Table 3: Phase Definitions for Cohort 2b

Phase	Phase #	Period	Period #	Interval		
				From	To	
Screening	1			Date and time of signing the informed consent form		
Regimen	2	Post-dose 1	1	Date and time of first vaccination	Minimum of:	
					a) 23:59 at the date of last contact (for early discontinuation)	
					b) 23:59 at the date of database cut-off in case of interim analysis	
					c) 23:59 on 28 days after the first vaccination (23:59 of day of vaccination + 28 days)	
					d) One minute prior to post-dose 2	
Follow-up 1	3			One minute after Post dose 1 period end	Minimum of:	
					a) 23:59 at the date of last contact (for early discontinuation)	
					b) 23:59 at the date of database cut-off in case of interim analysis	
					c) One minute prior to post dose 2	
Regimen	2	Post-dose 2	2	Date and time of second vaccination	Minimum of:	
					a) 23:59 at the date of last contact (for early discontinuation)	
					b) 23:59 at the date of database cut-off in case of interim analysis	
					c) 23:59 on Day 28 after the second vaccination (23:59 of day of vaccination + 28 days)	
Follow-up 2	4			One minute after Post-dose 2 period end	Minimum of:	
					a) 23:59 at the date of last contact (for early discontinuation)	
					b) 23:59 at the date of database cut-off in case of interim analysis	
					c) One minute prior to post booster 1	
Regimen	2	Post-booster 1	3	Date and time of first booster vaccination	Minimum of:	
					a) 23:59 at the date of last contact (for early discontinuation)	
					b) 23:59 at the date of database cut-off in case of interim analysis	
					c) 23:59 on Day 28 after the first booster vaccination (23:59 of day of vaccination + 28 days)	
Follow-up 3	5			One minute after Post-booster 1 period end	Minimum of:	
					a) 23:59 at the date of last contact (for early discontinuation)	
					b) 23:59 at the date of database cut-off in case of interim analysis	
					c) One minute prior to post booster 2	
Regimen	2	Post-booster 2	4	Date and time of second booster vaccination	Minimum of:	
					a) 23:59 at the date of last contact (for early discontinuation)	
					b) 23:59 at the date of database cut-off in case of interim analysis	

Phase	Phase #	Period	Period #	Interval	
				From	To
Follow-up 4	6			One minute after Post-booster 2 period end	c) 23:59 on Day 28 after the second booster vaccination (23:59 of day of vaccination + 28 days) Minimum of: a) 23:59 at the date of last contact (for early discontinuation) b) 23:59 at the date of database cut-off in case of interim analysis c) 23:59 at the date of last visit

Note: the end date of the regimen phase should be the end date of the last post dose period.

Adverse Events and selected other tables may display AEs (or other counts) by period. For such tables, active periods can be combined and additionally displayed. Depending on the primary regimen (one or two doses; presence or absence of booster doses), the active periods can be:

- “Post-Dose 1”
- “Post-Dose 2” (does not exist in Cohort 2a)
- “Post-Dose 1 and Post-Dose 2 Combined”, which refers to the “primary regimen”. If the primary regimen is a one-dose regimen (Cohort 2a), then this combined period will not exist and should also not be displayed.
- “Post-Booster 1” (only in cohorts 2a and 2b)
- “Post-Booster 2” (only in cohorts 2a and 2b)
- “Post-Dose 1 and Post-Booster Doses Combined”, which refers to the complete regimen including all the booster doses in Cohort 2a. It includes the 28-day period after each vaccination (dose 1, booster dose 1, and booster dose 2).
- “Post-Dose 1, Post-Dose 2 and Post-Booster Doses Combined”, which refers to the complete regimen including all the booster doses in Cohort 2b. It includes the 28-day period after each vaccination (dose 1, dose 2, booster dose 1, and booster dose 2).

For some tables, e.g. SAE tables, a period “Entire study” will be defined. This will be a combination of all the active phases and periods, so that it covers the time window from vaccination 1 up to and including the end of the study (per participant).

The primary endpoint includes SAEs from the first vaccination until 6 months after completion of the primary regimen for cohorts 2a and 2b. This will be a combined period of post-dose 1 and post-dose 1 Follow Up (FU) (for Cohort 2a) and a combination of post-dose 1, post-dose 1 FU, post-dose 2, and post-dose 2 FU (for Cohort 2b). This period will be labeled “Entire Primary Regimen” or similar in the outputs.

The exploratory endpoints include SAEs from the first booster vaccination time point until the end of the regimen for Cohort 2. This will be a combined period of post-booster 1 until the last follow-up period in Cohorts 2a and 2b. This period will be labeled “Entire Booster Regimen” or similar in the outputs.

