7.3. Primary Endpoint(s) Analysis

The primary endpoints in this study, are:

All participants in Cohorts 1, 2, and 3:

- Solicited local and systemic adverse events (AEs) for 7 days after each vaccination in the primary regimen
- Unsolicited AEs for 28 days after each vaccination in the primary regimen
- For the primary endpoint: Serious adverse events (SAEs) from the first vaccination until 1 year after the second vaccination for Cohorts 1 and 3, and until 6 months after the primary regimen for Cohort 2

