7.6.1. Adverse Events

7.6.2. Definitions

Solicited AEs shown in the tables are extracted from the investigator assessment pages (CE) of the CRF. For unsolicited AEs, only the AEs within the 28-day period following each vaccination will be presented in the safety tables except for SAEs, which will be captured and tabulated in the outputs covering the whole study period. All other collected unsolicited adverse events will be presented through listings.

Solicited administration site symptoms will be considered as related to the study vaccine (by definition).

The severity of the AEs will be classified as grade 1 to 4. Solicited events that are graded less than grade 1, are not considered as AE. In case no grades are available, the grading of the solicited events will occur according to the grading list in Appendix 3.

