7.6.4. Phase Allocation of Adverse Events

Solicited events are always allocated to the respective Post Dose period.

Step 1: Allocation of events to the periods:

Adverse events in the SDTM database are allocated to periods based on their start date/time. If the start date/time of an event falls between (or on) the start and stop date/time of a period, the AE is attributed to that period (treatment-emergent principle).

- In case of partial start or stop dates (i.e. time and/or day and/or month and/or year missing), the events are allocated to the periods using the available partial information on start and end date; no imputation will be done. If, for instance, the AE start date only month and year are available, these data are compared to the month and year information of the periods. This rule may lead to multiplication of the event as a consequence of its assignment to multiple periods.
- In case of a completely missing end date, the date is imputed by the cut-off date of the analysis for participants still ongoing in the study, and by the end date of the last period for participants who discontinued or completed the trial. In case of a completely missing start date, the event is allocated to the first active treatment phase (post dose 1 period), except if the end date of the AE falls before the start of the first active treatment phase (post dose 1 period).

Step 2: Combination of events:

Overlapping/consecutive events are defined as events of the same participant with the same preferred term which have at least 1 day overlap or for which the start date of an event is 1 day

^a In case this list of terms needs to be revised, the DPS will detail the revised list.

after the end date of the preceding event. Overlapping/consecutive events may be combined into one AE or not, according to the following rules:

- 1) If overlapping/consecutive events start in one of the following periods - Screening or post dose extension (i.e. non-active periods) - followed by an AE in - post-dose period (active period) - they are allocated to their respective periods and are considered as separate events.

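### The period that implements the Cohort 2 primary SAE endpoint has no 6-month end, so SAEs after 6 months can be counted in participants boosted late or never

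*SAP*

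**What the plan says.** Section 7.1.2 states the endpoint: "The primary endpoint includes SAEs from the first vaccination until 6 months after completion of the primary regimen for cohorts 2a and 2b". Section 7.3 gives the same limit: "until 6 months after the primary regimen for Cohort 2".

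Section 7.1.2 then fixes the derivation. For Cohort 2a: "This will be a combined period of post-dose 1 and post-dose 1 Follow Up (FU) (for Cohort 2a"). For Cohort 2b it is "a combination of post-dose 1, post-dose 1 FU, post-dose 2, and post-dose 2 FU (for Cohort 2b"). It adds: "This period will be labeled “Entire Primary Regimen” or similar in the outputs".

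The last component is Follow-up 1 in Table 2 (Cohort 2a) and Follow-up 2 in Table 3 (Cohort 2b). Each ends at the minimum of three times: the date of last contact for early discontinuation, the database cut-off for an interim analysis, and "c) One minute prior to post booster 1".

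Section 7.6.4 uses the start date to choose the period: "If the start date/time of an event falls between (or on) the start and stop date/time of a period, the AE is attributed to that" one. Section 7.6.2 confirms that SAEs beyond the 28-day windows are available, since it refers to "SAEs, which will be captured and tabulated in the outputs covering the whole study period".

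**The concern.** The endpoint has a calendar limit and the derivation does not. The two agree only when booster 1 falls exactly at 6 months, or when one of the other end terms happens to act by then.

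A participant whose booster 1 is late carries a window longer than the endpoint. A participant who completes the study without booster 1 meets none of the three end terms at the End of Study analysis, so the period has no defined end. That participant also never enters the Entire Booster Regimen period, so a late SAE has nowhere to go but the primary one.

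Under section 7.6 the denominator is the number of participants in the population and phase. It is not person-time, so nothing adjusts for unequal windows. At stake is whether the primary SAE table describes the endpoint named above it.

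**Working it through.** The SAP gives no figure for this period, so there is none to reproduce. The main check compares the texts; the arithmetic after it is illustrative.

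**1. End terms side by side**

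| End term | Endpoint (7.1.2, 7.3) | Table 2 Follow-up 1 | Table 3 Follow-up 2 | Final follow-up row of Tables 2 and 3 |
|---|---|---|---|---|
| 6 months after primary regimen | yes | no | no | no |
| Last contact (early discontinuation) | – | yes | yes | yes |
| Interim database cut-off | – | yes | yes | yes |
| One minute before booster 1 | – | yes | yes | – |
| Date of last visit | – | no | no | yes |

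The one limit that the endpoint states is absent from both implementing rows. The last-visit term exists in the SAP, but only in the final row of each table, which a participant without booster 1 does not reach.

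**2. Window lengths**

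Inputs: the change log's 24-month target days, Day 731 (2a) and Day 787 (2b), used only for scale; 30.4375 days per month, so 6 months is about 183 days and 12 months about 365. Working back 730 days, the primary regimen is complete on Day 1 in 2a (731 − 730) and Day 57 in 2b (787 − 730). Six months later is Day 184 in 2a and Day 240 in 2b, so the intended windows W are 183 and 239 days.

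Assumption: booster 1 is due at 6 months.

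| Situation | 2a, days (ratio to 183) | 2b, days (ratio to 239) |
|---|---|---|
| Booster 1 at 6 months | 183 (1.00) | 239 (1.00) |
| 30 days late | 213 (1.16) | 269 (1.13) |
| 60 days late | 243 (1.33) | 299 (1.25) |
| 90 days late | 273 (1.49) | 329 (1.38) |
| Never boosted, in analysis to 12 months after primary regimen | 365 (1.99) | 421 (1.76) |
| Never boosted, in analysis to 24 months after primary regimen | 730 (3.99) | 786 (3.29) |

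**3. Mean excess if a fraction f is never boosted and the rest are boosted on time**

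Relative excess = f × (T − W) / W, with f = 0.1, 0.2, 0.3 (assumed).

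- 2a, 12 months: f × (365 − 183)/183 = +10/20/30%.
- 2a, 24 months: f × (730 − 183)/183 = +30/60/90%.
- 2b, 12 months: f × (421 − 239)/239 = +8/15/23%.
- 2b, 24 months: f × (786 − 239)/239 = +23/46/69%.

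**4. Displayed risk in Cohort 2a**

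Assume a constant 3 SAEs per 100 person-years. Risk over t years = 1 − exp(−0.03t): 1.49% at 0.5 years, 2.96% at 1 year, 5.82% at 2 years. Displayed risk = (1 − f) × 1.49% + f × (risk at 1 or 2 years).

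- To 12 months: 1.64, 1.78 and 1.93% for f = 0.1, 0.2, 0.3.
- To 24 months: 1.92, 2.36 and 2.79%.

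**The case against.** The strongest reply is that the 6-month limit is stated twice, so a careful programmer would apply it, and that the open window rarely matters in practice. The period also ends at early discontinuation and at an interim cut-off. Under section 7.6.7, participants leave the main safety analyses at the ad hoc booster, and may already have left at unblinding or on receiving an unscheduled vaccine. The ad hoc booster was offered to all eligible participants. Section 7.6 provides no formal group comparisons, and section 7.6.3 keeps COVID-19-related SAEs out of the SAE tables.

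Much of this stands as a limit on size. It does not restore the endpoint. None of these exits is tied to 6 months, and an interim cut-off does not act at the End of Study analysis. Section 7.1.2 also says what the period will be, so a programmer who follows it literally and one who caps at 6 months would both be following the SAP, and would produce different tables.

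A reader might go further and infer three things that the SAP does not support:

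- That reported SAE percentages are inflated. They can be, but only if SAEs occur after 6 months in late- or never-boosted participants still in the main analysis. A booster 1 before 6 months would shorten the window.
- That regimens are compared over different lengths of time. This needs booster uptake or timing to differ by regimen, which the SAP does not show.
- That unboosted participants are counted for 24 months. Days 731 and 787 are target visits of a removed booster, not a stated end of follow-up.

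**Conclusion.** The mismatch is certain from the text and applies to both Cohort 2a and Cohort 2b: the stated derivation does not deliver the stated primary SAE endpoint, and no other section of the SAP repairs it. It should be corrected before the primary SAE table is relied on.

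The effect cannot be sized from the SAP, which gives no date for booster 1, no late or unboosted fraction and no SAE rate. The illustrative Cohort 2a risks range from barely different (1.6% against 1.5%) to nearly double (2.8%), depending wholly on the assumed unboosted fraction and follow-up. The relative excess is smaller in Cohort 2b, because its intended window already includes the interval between doses. Removals under section 7.6.7 pull towards the lower end.

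**What to change.** - Define Entire Primary Regimen directly by date: from first vaccination to the minimum of 23:59 on the date 6 months after the last primary-regimen vaccination and the existing end terms (last contact for early discontinuation, interim cut-off, one minute before booster 1).
- Leave the phase tables otherwise unchanged, but add 23:59 at the date of last visit to the minimum in Table 2 Follow-up 1 and Table 3 Follow-up 2, so that the phase closes for completers without booster 1.
- State that SAEs after the 6-month date and before any booster 1 count only towards the Entire study period.

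The cost is one derived period and one added line in each of two tables, using dates already held. The primary SAE table may show fewer events; those removed from it stay visible under Entire study.
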